### **8.2 Complete Remission with Incomplete Platelet Recovery (CRp)**

For patients to be classified as being in CRp, they must achieve CR except for incomplete platelet recovery ( $< 100 \times 10^9/L$ ).

### **8.3 Complete Remission with Incomplete Hematological Recovery (CRi)**

For patients to be classified as being in CRi, they must fulfill the criteria for CR except for incomplete hematological recovery with residual neutropenia (ANC  $\leq 1 \times 10^9/L$ ) with or without thrombocytopenia (platelet count  $< 100 \times 10^9/L$ ). In addition, patients do not need to be RBC or platelet transfusion independent (modification to Cheson criteria).

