## 7.2 Evaluation During Treatment

7.2.1 Physical exam on day 1 of each cycle ( $\pm$  1 days) for the first 4 cycles, then every 1-2 cycles.

7.2.2 CBC, platelet count, hemoglobin, differential at least once weekly for the first 3 cycles, then every 2-4 weeks (differential can be omitted if WBC is  $\leq 0.5 \times 10^9/L$ ). Outside labs may be used, but the PI/Treating physician must review all protocol specific outside lab results and determine the clinical significance of abnormal values then sign/date the results or dictate this process in the medical record.

7.2.3 Creatinine, BUN, total bilirubin, ALT, AST weekly ( $\pm 4$  days) for the first 3 cycles, then every 2-4 weeks.

7.2.4 Laboratory tests can be ordered more frequently if mandated by development of peripheral blast/blood counts or electrolyte/liver function test abnormalities.

7.2.5 Bone marrow aspiration for differential and PCR for FLT3 on day 28 ( $\pm 7$  days) of cycle 1, day 28 of cycle 3 ( $\pm 7$  days), then every 1-3 cycles. Bone marrow tests can be ordered more frequently if mandated by development of peripheral blood counts. No repeat bone marrow is necessary if nonresponse or progressive disease can be unequivocally diagnosed from peripheral blood tests or, in patients with a WBC  $< 0.3$  if the bone marrow test is considered noncontributory by the investigator at any time point.

- 7.2.6 Concomitant medication data will not be collected or entered into the case report form (PDMS is the case report form for this study). Concomitant medication data will not be collected or entered into the case report form except for concomitant hydroxyurea if administered during the first cycle; however, the subject's medication record will contain a list of concomitant medications.
- 7.2.7 12-lead EKG will be performed on day 1 ( $\pm 1$  day) of each cycle for the first 4 cycles, then every 1-3 cycles
- 7.2.8 Peripheral blood (up to 35 cc each time) and bone marrow (up to 10 cc each time) for pharmacodynamic studies (Optional) as defined in section 6.2 on
- **Peripheral blood:**
  - Prior to first dose of selinexor at baseline (Cycle 1 Day 1) as per section 7.1.10.
  - Cycle 1 Day 1: 4 (+/- 1) hours after the first dose of selinexor to evaluate (1) XPO1 induction/inhibition in leukocytes and (2) plasma protein/cytokine analysis

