## **8.0 CRITERIA FOR RESPONSE**

Response criteria will be modified from the International Working Group for AML. Responders are patients who obtain a Composite Complete Remission Rate (CRc) with or without cytogenetic response, hematologic improvements, and morphologic leukemia-free state. CRc rate is defined as the confirmed remission rate of all complete and incomplete CRs (i.e., CR+ CRp + CRi).

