### **8.1 Complete Remission (CR)**

For patients to be classified as being in CR, they must have bone marrow regenerating normal hematopoietic cells and achieve a morphologic leukemia-free state and must have an ANC  $> 1 \times 10^9/L$  and platelet count  $\geq 100 \times 10^9/L$ , and normal marrow differential with  $< 5\%$  blasts, and patients will be red blood cell (RBC) and platelet transfusion independent (defined as 4 weeks without RBC transfusion and 1 week without platelet transfusion). There should be no evidence of extramedullary leukemia.

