## 11.2 Phase II

The primary objective of the phase II is to evaluate the efficacy of the combination. The study has two cohorts (maximum of 20 patients for each cohort): (1) FLT3-ITD and –D835 mutated relapsed/refractory AML previously exposed to any FLT3 inhibitor, and (2) FLT3-ITD and –D835 mutated relapsed/refractory AML with no prior exposure to any FLT3 inhibitor.

For all the cohorts, the primary endpoint is the achievement of CRc (CRc=CR/CRp/CRi) at any time during the first three cycles of therapy and toxicity assessed at the end of one cycle of therapy. CRc and toxicity will be monitored simultaneously using the Bayesian approach of Thall, Simon, Estey (1995, 1996) and the extension by Thall and Sung (1998) separately for each cohort. Multic Lean Desktop (version 2.1) was used to generate the stopping boundaries and the OC tables for futility and toxicity monitoring.

- **Cohort #1: Patients with relapse FLT3-ITD and –D835 mutant AML (FLT3 inhibitor naïve cohort):**

The historical data suggested a CRc rate of 20% for this population and the target CRc with selinexor and sorafenib combination is 35%. The treatment will be considered worthy of further investigation if it elicits an increase in CRc to 35% with acceptable toxicity. A >30% therapy related non-hematological grade 3/4 toxicity rate is considered unacceptable. Given this, we will stop enrollment into this cohort if the observed patients' data suggest that:

- 1)  $\Pr(\text{CR}_{cE} > \text{CR}_{cH} + 0.15 | \text{data}) < 0.025$  or
- 2)  $\Pr(\text{TOX}_E > 0.30 | \text{data}) > 0.90$

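### Sections 8.1 to 8.3 leave a non-monotone gap in CRc: a marrow remission with ANC above 1 and a recent transfusion is not CR, CRp or CRi, while the same patient with ANC of 1 or less is CRi

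*Combined protocol and SAP*

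**What the plan says.** Section 11.2 states that "the primary endpoint is the achievement of CRc (CRc=CR/CRp/CRi) at any time during the first three cycles of therapy". Section 8.0 limits CRc to the same three categories: "CRc rate is defined as the confirmed remission rate of all complete and incomplete CRs (i.e., CR+ CRp + CRi". The three definitions treat transfusion differently.

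- **CR (8.1):** ANC above 1 x 10^9/L, platelets at least 100 x 10^9/L, under 5% marrow blasts, no extramedullary disease, and transfusion independence, "defined as 4 weeks without RBC transfusion and 1 week without platelet transfusion".
- **CRp (8.2):** "they must achieve CR except for incomplete platelet recovery". The only stated exception is platelets below 100, so the transfusion condition carries over.
- **CRi (8.3):** "they must fulfill the criteria for CR except for incomplete hematological recovery with residual neutropenia" (ANC of 1 or less), with or without low platelets. Here alone "patients do not need to be RBC or platelet transfusion independent", which the protocol labels a modification of the published criteria.

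CRc also feeds the futility rules in section 11.2 (Tables 6 and 9). Section 8.8 scores best response over the first three cycles. Section 7.2.5 schedules marrows at cycle 1 day 28 and cycle 3 day 28, each within 7 days, with more allowed if blood counts call for them.

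**The concern.** The transfusion waiver is tied to neutropenia. Take two patients with the same remission marrow and the same red-cell transfusion two weeks ago. The one with ANC 0.9 is CRi and counts as a success. The one with ANC 1.2 fits none of the three categories and counts as a failure. At a given assessment, better neutrophil recovery lowers the score.

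The timing makes this state possible. At the cycle 1 marrow ("Bone marrow aspiration for differential and PCR for FLT3 on day 28"), four weeks without red cells means none since about the start of treatment. Section 5.6.3 permits red-cell and platelet transfusion and growth factors, so ANC can recover while transfusion continues.

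Each futility decision turns on one or two responders among 5, 10 or 15 patients. Whether such a patient counts can therefore decide whether a cohort continues. Without a written rule, that call would be made case by case in open-label, single-arm cohorts of 20.

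**Working it through.** **Step 1: enumerate the states.** Hold fixed a marrow that meets 8.1 and no extramedullary disease. Vary ANC (above 1, or not), platelets (at least 100, or not), red-cell-free for 4 weeks (yes/no) and platelet-transfusion-free for 1 week (yes/no). This gives 16 states. All 8 with ANC of 1 or less are CRi. The 8 with ANC above 1 are:

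| Platelets | Red-cell-free 4 wk | Platelet-transfusion-free 1 wk | Category |
|---|---|---|---|
| at least 100 | yes | yes | CR |
| at least 100 | yes | no | none |
| at least 100 | no | yes | none |
| at least 100 | no | no | none |
| below 100 | yes | yes | CRp |
| below 100 | yes | no | none (CRp on a lenient reading) |
| below 100 | no | yes | none |
| below 100 | no | no | none |

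Six of the 8 fit no CRc category. If incomplete platelet recovery in 8.2 is read to include platelet-transfusion dependence, 5 remain. No reading places ANC above 1 with a red-cell transfusion in the last 4 weeks. PR does not catch these patients either, because 8.4 requires 5% to 25% marrow blasts. They can be recorded as morphologic leukemia-free state (8.5) or marrow clearance (8.8), and neither is part of CRc.

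**Step 2: reproduce the plan's figures.** The cohorts are named here, not numbered, because sections 3.1 and 11.2 number them in opposite order. Looks are after 5, 10 and 15 patients.

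- Naive cohort, prior Beta(0.4, 1.6): stop if Pr(p > 0.35 | data) < 0.025. The posterior probability is 0.0139 at 0/5, 0.0215 at 1/10 and 0.0192 at 2/15 (stop), against 0.1525 at 1/5, 0.1043 at 2/10 and 0.0728 at 3/15 (continue). This is Table 6.
- Failure cohort, prior Beta(0.2, 1.8): stop if Pr(p > 0.20 | data) < 0.025. The values are 0.0279 at 0/5 (continue), and 0.0065 at 0/10 and 0.0017 at 0/15 (stop). This is Table 9.
- Toxicity boundaries as tabled: 4, 6, 8 (Table 7) and 4, 5, 7 (Table 10).

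With response and toxicity independent, Pr(stop early) = 1 - C_R x C_T. C_R and C_T are the exact binomial probabilities of passing all three looks for response and for toxicity. At the bolded cells:

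- Naive, 35% response, 30% toxicity: 1 - 0.83187 x 0.91555 = 0.2384 (Table 8: 0.2384).
- Failure, 20% response, 30% toxicity: C_R = 1 - 0.8^10 = 0.89263, because 0/15 implies 0/10. Then 1 - 0.89263 x 0.80433 = 0.2820 (Table 11: 0.2820).

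All 50 entries of Tables 8 and 11 reproduce to four decimals. The tables are not in error.

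**Step 3: effect of the gap.** Let f be the share of remissions that stay in the gap at every assessment in the first three cycles. The documents do not give f, so a range is assumed. Scored CRc is the target x (1 - f), with toxicity at 30%.

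| f | Naive: scored CRc | C_R | Stop early | Failure: scored CRc | C_R | Stop early |
|---|---|---|---|---|---|---|
| 0 | 35% | 0.83187 | 23.8% | 20% | 0.89263 | 28.2% |
| 5% | 33.25% | 0.80355 | 26.4% | 19% | 0.87842 | 29.3% |
| 10% | 31.5% | 0.77149 | 29.4% | 18% | 0.86255 | 30.6% |
| 25% | 26.25% | 0.65106 | 40.4% | 15% | 0.80313 | 35.4% |

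For example, naive at 10%: 1 - 0.77149 x 0.91555 = 0.2937.

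**The case against.** The strongest reply is that the gap may hardly matter. Several parts of it stand.

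- **Frequency.** A reader might infer that the gap is common because most patients are transfused. Section 5.6.3 says that most patients enter with neutropenia, thrombocytopenia or both, but it only permits transfusion when clinically indicated. Persisting neutropenia would also put a remitter in CRi, outside the gap.
- **Best response.** A patient in the gap at day 28 can still score later, either transfusion-free or with a low ANC, and an earlier CRi is not cancelled when ANC rises. The reversal holds between patients at one assessment; only a patient in the gap throughout is lost.
- **Other reporting.** The patient is still recorded as morphologic leukemia-free state. Section 8.0 mentions that state in its sentence on responders, and 11.3 analyses an ORR that it does not define, so the patient might count there. CRc remains CR, CRp and CRi.
- **Direction of bias.** A reader might infer that CRc is biased downward. That would require the 35% and 20% targets to include such patients. If they were set on section 8 as written, nothing is lost. The documents do not say how the historical 20% and 10% classified transfused patients.
- **Deliberate choice.** The waiver is a declared modification. That explains accepting transfused remissions, but not why only neutropenic patients may have them.

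None of this assigns a CRc category to the patient with ANC above 1 and a recent red-cell transfusion.

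**Conclusion.** The gap is real on the plain text of 8.1 to 8.3, and it makes the primary endpoint and the futility count non-monotone in ANC. For red-cell transfusion no reading closes it; for platelet transfusion alone with platelets below 100, a lenient reading of 8.2 does.

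Its size cannot be derived from the documents. Across assumed shares of 5% to 25%, early stopping at 30% toxicity rises by 2.6 to 16.6 percentage points in the naive cohort (23.8% to 26.4% or 40.4%) and by 1.1 to 7.2 points in the failure cohort (28.2% to 29.3% or 35.4%). These figures assume that the targets were meant to include such patients, that the share applies after best-response scoring, and that response and toxicity are independent. At the low end the effect is small. The documents do not support a claim that the gap is frequent or that CRc is certainly understated.

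**What to change.** Reword 8.3 so that CRi covers every patient who meets the CR marrow and extramedullary criteria but lacks ANC recovery, platelet recovery or transfusion independence, and is not already CRp, whatever the ANC. State in 8.2 whether CRp requires transfusion independence. CR, CRp and CRi then cover all such marrow remissions, and a higher ANC can no longer remove a patient from CRc.

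Narrowing the waiver would also restore monotonicity, but it would undo a modification that the protocol declares. Widening CRi fits the stated intent better.

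The cost is about one sentence in each section. The downside is that CRc becomes slightly more inclusive. Before the rule is used in monitoring or analysis, the sponsor should confirm that the historical rates (20% naive, 10% failure) and the targets (35% and 20%) use the same definition. If they do, the boundaries in Tables 6 and 9 need no change.

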### **8.4 Partial Remission (PR)**

For patients to be classified as being in PR, they must have bone marrow regenerating normal hematopoietic cells with evidence of peripheral recovery with no (or only a few regenerating) circulating blasts and with a decrease of at least 50% in the

percentage of blasts in the bone marrow aspirate with the total marrow blasts between 5% and 25%.

### **8.5 Morphologic leukemia-free state:**

Bone marrow:  $\leq 5\%$  myeloblasts

**8.6 Hematologic Improvement (HI):** Hematologic response must be described by the number of positively affected cell lines.

- ◆ **Erythroid response (E)** (pretreatment Hgb  $< 11$  g/dL)  
Hgb increase by  $\geq 1.5$  g/dL
- ◆ **Platelet response (P)** (pretreatment platelets  $< 100 \times 10^9/L$ )  
Absolute increase of  $\geq 30 \times 10^9/L$  for patients starting with  $> 20 \times 10^9/L$  platelets  
Increase from  $< 20 \times 10^9/L$  to  $> 20 \times 10^9/L$  and by at least 100%
- ◆ **Neutrophil response (N)** (pretreatment ANC  $< 1.0 \times 10^9/L$ )  
At least 100% increase and an absolute increase  $> 0.5 \times 10^9/L$
- ◆ **Blast response (B)**  
 $\geq 50\%$  reduction in peripheral blood or bone marrow blasts but still  $> 5\%$

### **8.7 Recurrence of Disease**

Relapse after CR is defined as a reappearance of leukemic blasts in the peripheral blood or  $\geq 5\%$  blasts in the bone marrow aspirate not attributable to any other cause or reappearance or new appearance of extramedullary leukemia. Relapse after PR is similarly defined with reappearance of significant numbers of peripheral blasts and an increase in the percentage of blasts in the bone marrow aspirate to  $> 25\%$  not attributable to any other cause or reappearance or new appearance of extramedullary leukemia.

### **8.8 Best Response measurement**

Response will be measured and defined for primary endpoints as the best response achieved during the first 3 cycles of therapy, or at time off study, for those patients discontinuing treatment before the completion of 3 cycles of therapy. Best response is defined to be the best-measured response (CRc=CR+CRp+CRi, PR, or marrow clearance) post-treatment up to that time. Best response will also be evaluated for the full treatment period using all assessments up to and including treatment discontinuation.

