#### **Phase II**

1. To determine the composite CR (CRc) rate including CR (complete remission) + CRp (complete remission with incomplete platelet recovery) + CRi (complete remission with incomplete count recovery) within 3 months of treatment initiation in FLT3-ITD and –D835 mutated patients with relapsed/refractory AML.

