such patients achieve marrow responses to *FLT3* inhibitors, with 20-30% bridged to allogeneic stem cell transplant. Responses to *FLT3* inhibitors last 3-6 months and are invariably transient (except among patients who undergo transplantation) due to the emergence of resistance. The primary cause of resistance is the acquisition of point mutations in the *FLT3* kinase domain (KD). Heidel et al first to identified point mutations in the *FLT3-ITD* KD as a mediator of resistance to the *FLT3* inhibitor midostaurin. They reported a single amino acid substitution at position 676 (N676K) within the *FLT3* KD as the sole cause of resistance to midostaurin in a patient with AML. Acquired point mutations in the KD may be preexisting or acquired after exposure to the *FLT3* inhibitors as has been shown with midostaurin. Homology modeling has identified two main types of *FLT3* mutations, namely TKD1 mutations involving the ATP-binding (hinge regions) and the TKD2 mutations involving the activation loop. Non-mutational mechanisms of resistance include up-regulation of compensatory pathways including the MAPK/ERK, *PI3K/Akt/mTOR*, *FOXO3A*, *SYK*, and *STAT5/PIM* pathways, up-regulation of the *FLT3* ligand or receptor, mutations in other kinases (e.g. *CBL*), activation of anti-apoptotic proteins *BCL2*, *MCL1* and *BCL-x(L)*, and tumor microenvironment mediated resistance.

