### **9.1.4 Follow-Up at Treatment Discontinuation or Early Withdrawal**

Patients who discontinue treatment for any reason should complete end-of-treatment procedures when possible. End of treatment procedures will include a physical examination, CBC with differential and platelets and a limited chemistry profile (total bilirubin, serum creatinine, SGPT or SGOT). A bone marrow aspiration may be recommended only if non-response or progressive disease cannot be unequivocally diagnosed from peripheral blood. Although treatment will be discontinued at that time, all patients who do not withdraw consent for follow-up, die, or become lost to follow-up, will remain on study for follow-up evaluations. Subject will be followed for toxicity for at least 30 days after the last protocol treatment. The 30-day (+/-7 days) follow-up visit will be scheduled as a clinic visits for clinical evaluation and physical examinations. If the patient cannot make it to the MDACC clinic for this visit, the required follow up treatment procedures may be done with a local physician and the records forwarded to MDACC. The research nurse will contact the patient by telephone and get a verbal assessment of the patient's condition. The phone conversation will then be documented in the patient's charts.

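### Early stoppers can count as CRc or as failures depending on the section, and nothing ends response credit at transplant or new anti-leukemic therapy

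*Combined protocol and SAP*

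**What the plan says.** - **Section 8.8, primary endpoint.** Best response is the best achieved in the first 3 cycles, "or at time off study, for those patients discontinuing treatment before the completion of 3 cycles of therapy". It is the best-measured response "post-treatment up to that time".
- **Section 8.8, full treatment period.** Best response is also evaluated "using all assessments up to and including treatment discontinuation". The section therefore has two different end points.
- **Section 9.1.4.** Patients who stop treatment and do not withdraw consent, die or become lost "will remain on study for follow-up evaluations". On marrow at the end of treatment: "A bone marrow aspiration may be recommended only if non-response or progressive disease cannot be unequivocally diagnosed from peripheral blood". No marrow is scheduled after that visit.
- **Section 1.1, Phase II.** The objective is CRc "within 3 months of treatment initiation in FLT3-ITD" and D835 mutated patients. This is a calendar limit.
- **Section 11.2.** "the primary endpoint is the achievement of CRc (CRc=CR/CRp/CRi) at any time during the first three cycles of therapy". This is a limit by cycles of study therapy.
- **Section 11.3.** Patients who leave the study before finishing all cycles are failures in the primary analysis.

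No passage says how a response first seen after HSCT or new anti-leukemic therapy is counted. Adverse-event recording does have a new-therapy cut-off (section 2.2.2, Potential Risks). Transplant is foreseen, since the number bridged to HSCT is a secondary objective.

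**The concern.** The response window for early stoppers depends on what off study means. Under 9.1.4, stopping treatment does not take a patient off study. A patient who stops in cycle 1 or 2 without remission, then receives a transplant or another therapy and remits, would on the words of 8.8 have a primary best response of CR. The same patient would not be a responder for the full treatment period, because that window has already closed. The primary window can thus outlast the full-treatment window.

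CRc drives the futility rule and is set against benchmarks of 20% (inhibitor-naive cohort) and 10% (inhibitor-failure cohort). If its value for early stoppers depends on which section the analyst follows, the stopping decisions and the reported rate depend on it too.

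**Working it through.** **1. The plan's own figures.** Boundaries were derived from beta-binomial posteriors at 5, 10 and 15 patients.

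- Naive cohort: prior Beta(0.4, 1.6), stop if Pr(CRc > 0.35) < 0.025. With 0 of 5 the posterior probability is 0.0139, with 1 of 10 it is 0.0215, and with 2 of 15 it is 0.0192. One responder more gives 0.1525, 0.1043 and 0.0728. This is Table 6.
- Failure cohort: prior Beta(0.2, 1.8), stop if Pr(CRc > 0.20) < 0.025. With 0 of 5 it is 0.0279 (no stop), with 0 of 10 it is 0.0065, and with 0 of 15 it is 0.0017. One responder gives 0.1218 at 10 and 0.0423 at 15. This is Table 9.
- Exact stopping probabilities, with response and toxicity independent, are 0.2384 (Table 8: response 35%, toxicity 30%) and 0.2820 (Table 11: response 20%, toxicity 30%). Both equal the stated values. The design figures are not in dispute.

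**2. The sections side by side.** Patient A stops in cycle 2 without CRc and has a first CR after HSCT or new therapy, still within 3 months of starting. Patient B reaches CRc at the end of cycle 1 and then stops for HSCT.

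| Rule | Patient A | Patient B |
|---|---|---|
| 8.8, primary | CRc if read literally; not CRc if off study means off treatment | CRc |
| 8.8, full treatment period | not CRc | CRc |
| 1.1 | CRc (calendar limit only) | CRc |
| 11.2 | not CRc on the natural reading | CRc |
| 11.3, dropout = leaving the study | rule does not apply | rule does not apply |
| 11.3, dropout = stopping treatment | failure | failure |

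If patient A remits after 3 months, 1.1 excludes the remission and the literal 8.8 still includes it. On the second reading of 11.3, all the cycles could mean up to 24 (section 5.3.1), so patient B's genuine remission would be lost.

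**3. Size per patient.** 1/20 = 5 points. The targeted gains are 35 − 20 = 15 points (three patients) and 20 − 10 = 10 points (two patients). In the failure cohort the futility stop needs 0 responders at 10 or 15, so one credited remission averts it. In the naive cohort one is enough when the count sits exactly on the Table 6 boundary.

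**4. Illustration under assumptions.** Let *e* be the share of non-responders who stop before the end of cycle 3, and *s* the share of those who remit on later therapy. Neither is in the documents. Apparent CRc = p₀ + (1 − p₀)·e·s. Toxicity is set at 30%.

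- e = s = 0.3, naive: 0.20 + 0.80 × 0.09 = 0.272. Early stopping falls from 0.578 to 0.381.
- e = s = 0.3, failure: 0.10 + 0.90 × 0.09 = 0.181. Early stopping falls from 0.476 to 0.305.
- e from 0.2 to 0.5 and s from 0.1 to 0.4: apparent CRc is 21.6–36.0% (naive) and 11.8–28.0% (failure). Early stopping is 0.529–0.225 and 0.425–0.226.

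For each assumed pair this is an upper bound, because every later remission is taken as measured and known by the interim looks.

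**5. The opposite direction.** Suppose 11.3 turned 20–30% of true responders into failures at a true CRc of 35% in the naive cohort (assumed). Counted CRc is 0.35 × 0.8 = 0.28 to 0.35 × 0.7 = 0.245. Early stopping rises from 0.238 to 0.363–0.448.

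**The case against.** The strongest reply is that off study in 8.8 simply means off treatment. The clause concerns patients who stop treatment, and the protocol often uses study in that sense: 3.5 and 11.1 allow dose escalation for patients still on study, 5.1.1 gives sorafenib for the length of the study, and 4.1.9 bars other anti-leukemic agents during it. Section 11.2 ties CRc to cycles of study therapy, and 1.1 caps it at 3 months. CR also needs a marrow, and none is scheduled after the end-of-treatment visit. The 5-year follow-up in 7.2.12 is for survival, in patients with an objective response, so it would not capture a later remission in a non-responder.

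Much of this stands. It makes the literal reading less likely to be intended and the affected cases fewer. It does not settle the rule. Section 9.1.4 uses study in the wider sense, and 8.8 is the only passage that sets the response window specifically for patients who stop before 3 cycles. A transplant or salvage remission can fall inside 3 months, and a marrow taken in routine care is not excluded.

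A reader might go further and infer an upward bias of known size, with "20-30% bridged to allogeneic stem cell transplant" as the expected share. The documents do not support that. The figure is background on FLT3 inhibitors generally and is reported beside marrow responses of 40–50%. Patients bridged while already in CRc count anyway. Section 11.3 may push CRc down instead of up.

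**Conclusion.** The point holds as an inconsistency in the definition of the primary endpoint. Sections 1.1, 8.8, 11.2 and 11.3 can classify the same early stopper differently, and no rule excludes a remission first documented after HSCT or new anti-leukemic therapy.

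What follows from the documents alone is the 5 points per misclassified patient and the single remission that averts the Table 9 stop. The direction and overall size of the bias cannot be derived from them. The ranges for apparent CRc and early stopping rest on assumed shares.

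It would also be too strong to say that later therapy would reproduce the target gain. Over the assumed range the naive cohort passes 35% only at the extreme corner, where half of the non-responders stop early and 40% of those remit and are counted. Whether the 20% and 10% benchmarks counted such remissions is not stated either. The point should be fixed because the endpoint drives futility and the repair is small.

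**What to change.** In 8.8, replace the off-study clause with treatment discontinuation, defined as the last assessment on or before the end-of-treatment visit and before HSCT conditioning or any new anti-leukemic therapy. Use the same window in 1.1, 11.2 and 11.3. Then state three things:

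- a CRc documented by that point still counts when the patient then stops, for example for HSCT;
- a response first documented after that point does not count as CRc for the primary endpoint;
- the 11.3 failure rule applies only to patients without a documented CRc by then.

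Rewording 8.8 alone is not enough, because 11.3 could still fail a patient who remitted and then went to transplant. The change is to an analysis definition and leaves patient care, sample size and stopping boundaries as they are. The cost is a few sentences, and the CRc rate may come out slightly lower.
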